1.10 Timetable/Schedule of Events

We have included the study timelines below.

2.0 Project Management

We have the necessary resources for this project. It has been funded by the NIH.

2.2 Research Staff Training

We will conduct training for the enumerators conducting the data collection as part of this study. During the enumerator training, we will use the Johns Hopkins School of Public Health Human Subjects Research Ethics Field Training Guide (2010) to train data collectors in human subjects research ethics, and will provide them with information about the project such that they would be qualified to provide information about the study and answer questions that participants may ask. There does not appear to be a similar training guide specific to Rutgers University.

Please note: Wherever possible, we will work with enumerators we have worked with in previous studies.

2.3 Other Resources

We received funding for this project through the National Institutes of Health Research. We have the necessary resources to engage in this research.

2.4 Research Sites

We have uploaded Form HRP-285 to this IRB application. The study sites for this project include: Thies, Diourbel and Fatick regions of Senegal. We will be conducting the study in 104 villages.

3.0 Multi-Center Research

Not applicable.

4.0 Subject Considerations

4.1 Subject Selection and Enrollment Considerations

A. Method to Identify Potential Subjects

Cognitive testing: Our local partner will help us to identify potential participants for the cognitive testing of the IYCF messages. These individuals will be purposively selected to ensure that we include a sufficient number of mothers and fathers. Our local partners have close ties with the communities we will be working in and are able to easily identify potential study participants from their existing networks. In addition, we will use snowball sampling (if necessary) to identify additional participants. Once the potential participants have been identified by our in-country partners, our partners will describe the project to them and seek their consent to participate.

cRCT: We plan to recruit 510 mother, father and child triads in 104 villages in three regions of Senegal (Thies, Diourbel and Fatick) as part of our cluster-randomized control trial. [name] has previously worked in the study communities and has experience recruiting study participants from within them. We will employ the same methods as we have in the past in order to recruit participants to this study.

We will begin the recruitment process by first getting approval from the head of the village to conduct the study in the respective village. This is customary in these villages and is important for ensuring buy-in from the community. We will then ask for approval from the President of the village farming group. Each of the 104 villages included in the study have an established farming group. We will recruit participants from the farming groups in each of the villages. We have previously worked closely with the Presidents of each of the farming groups. We will ask the President of the farming group to share the list of households in the farming group. We will then identify all households in the farming group with a child between 6-19 months (at the time of the baseline data collection), and we will then randomly select five households per farming group to participate in the study. In order to facilitate our recruitment, we will plan initial fieldwork that will enable us to update our existing lists of households in the farming groups and the

number of households with children between 6-19 months at the time the intervention will begin (June 22). This will enable us to ensure that we have an up-to-date sampling frame. We will oversample to ensure that we are able to recruit 5 households/triads per village.

At the time of our baseline surveys, the President of the farmers group will then introduce us to each of the household heads. We will explain the study procedures to the household head, the woman and her husband before asking for their consent to participate in the study. Given the local customs in Senegal it is necessary to first explain the study to the household head, even though they will not be participating in the study. If the household head does not want members of their household to participate we will stop the recruitment process. Based on our previous experience, we were able to recruit participants from the study villages efficiently.

Informed consent will be collected during recruitment or immediately prior to participation in the baseline survey in the language spoken by the participant. The enumerators will meet with participants in their homes or another location in the community, as preferred by the participant. We will make every effort to obtain consent in privacy (without any peers or family members present, as described above). At the end of the recruitment and consent process, we will coordinate with the participant to schedule the timing and location of the survey. Based on our previous work in these communities, we anticipate a very high participation rate, and do not foresee difficulties in recruiting our study sample.

Process evaluation: A smaller purposive sample of approximately 45 mothers and fathers, implementation project staff and CHWs will be included in Aim 2 of the project as part of the in-depth semi-structured interviews/focus groups conducted in the process evaluation. We will purposively select three villages from each region (n total = 9 villages) in order to maximize variation in village characteristics such as size, distance to urban settings, distance to markets, etc. Interviewees will be purposively selected from the list of all mothers and fathers receiving the voice messages in each of these villages to ensure variation in participant socio-demographics (e.g., household size, parity, age, etc.) as well as key people involved in the intervention's implementation.

B. Recruitment Details

Cognitive testing: Our local partners and enumerators will recruit potential subjects using their existing networks. Initial contact with the potential subjects will be made face-to-face, but at a safe distance (i.e., 6 feet) in public outdoor spaces within the study communities. The following recruitment script will be used to recruit potential participants:

- *Verbal recruitment script:* Good morning/afternoon. My name is _____ and I am working with researchers at Rutgers University, a university in the United States, and the Institut de Recherche en Santé, de Surveillance Epidémiologique et de Formation. You were recommended as someone who might be interested in participating in an interview with us. We would like to learn about your understanding of infant and young child feeding messages. Are you interested in learning more about this project? If so, I can tell you more about the interview and answer any questions you have about the project. I also have an information letter about the project that I can go over with you. If you agree to participate in the project, I will organize with you to find a

good time to schedule a 30-45 minute interview.

cRCT and process evaluation: Our team of local enumerators will recruit study participants for the cRCT. They will first explain the study procedures to the household head, the mother and father before asking for their consent to participate in the study. At this time, we will also describe the intervention to the participant, providing them with information regarding the timing of the intervention as well as the details of what the intervention entails. The enumerators will meet with participants in their homes or another location in the community, as preferred by the participant. We will make every effort to obtain consent in privacy (without any peers or family members present, as described above). At the end of the recruitment and consent process, we will coordinate with the participant to schedule the timing and location of the survey. We will obtain consent for participation in the process evaluation at the time of cRCT consent. However, at the time of the endline survey we will ask participants again whether they are willing to participate in the semi-structured interviews.

- *Verbal recruitment script:* Good morning/afternoon. My name is _____ and I am working with researchers at Rutgers University, a university in the United States, and the Institut de Recherche en Santé, de Surveillance Épidémiologique et de Formation. We are doing research to measure the impact of a mobile messaging intervention about how to best feed your baby. Are you interested in learning more about this project? If so, I can tell you more about the project and answer any questions you may have. I also have an information letter about the project that I can go over with you. If you agree to participate in the project, I will organize with you to find a good time to schedule a 45 minute interview.

C. Subject Screening

- **Inclusion Criteria**

Cognitive testing: We will include adults who are parents to young children. We will not have restrictions based on ethnicity. In addition, we will only include people who have the ability and mental capacity to consent to their participation (i.e., not a member of a vulnerable group that is unable to voluntarily provide consent, such as a prisoner, or someone with limited mental ability, such as a person with dementia).

cRCT: Within each of the participating villages, the farming group will be used as the sampling frame for our sample. Thus, in order to be included in the study one of the members of the household will need to be a member of the village farming group. Additional inclusion criteria include: 1) mothers and fathers that have a child between the ages of 6 to 19 months at baseline and 2) have access to a mobile phone. Women and men included in the study will be 16 years of age or older. In order to be included in the study both the mother (or primary female caregiver) and father (or male primary caregiver) need to consent to participate.

We will only include people who have the ability and mental capacity to consent to their participation (e.g. not a member of a vulnerable group that is unable to voluntarily provide consent, such as a prisoner, or someone with limited mental ability, such as a person with dementia). The exclusion criteria includes households that do not have a child between the ages of 6 to 19 months old at baseline. In order to determine whether a household is eligible for

participation, we will ask the household head if there is a child 6 to 19 months in the household. If there is more than one child between 6-19 months, we will select the youngest child to participate in the study. We will then confirm the child's age using a vaccination card or birth certificate. We will also ascertain the age of the mother and father to ensure that they are 18 years of age or older.

Process evaluation: After the completion of the endline survey, enumerators will ask participants if they would be willing to participate in a semi-structured interview as part of the process evaluation. Of those that indicate their willingness to participate, we will purposively select participants in order to ensure that we include variation in terms of the socio-demographic characteristics of participants.

- **Exclusion Criteria**

Exclusion criteria include parents of children over the age of 24 months, those without access to a mobile phone and those that are cognitively impaired.

D. Privacy Protections

We do not anticipate any risks to participants or their privacy in the recruitment process. Furthermore, the recruitment process will be completed one-on-one with the participants such that their decision to participate or not will be theirs alone and any questions or concerns they have about the project will not be shared. The mother and father being recruited in the study will be recruited separately in the household compound. The enumerator will explain the study to both the parents together but will then take each potential participant aside in order to obtain consent. One enumerator will visit each household. If the layout of the household compound (which normally includes huts within a fenced off area of the compound) does not permit privacy from other family members, the enumerator will take the potential participant outside of the household compound in order to obtain consent.

We have previously worked in these study communities and have not had any problems in terms of the gender of the enumerators in terms of conducting surveys. We do not anticipate any problems in terms of allowing women to be alone with enumerators if they are male.

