1.3 Research Design and Methods

This project involves five main components: 1) identification of role models in villages included in our pilot study²¹ whose experiences related to IYCF will be recorded and included in the messaging intervention; 2) cognitive testing of the IYCF messages to ensure clarity; 3) a cluster randomized control trial (cRCT) of an mHealth IYCF messaging intervention (text and voice messages) that includes information about IYCF best practices that will be delivered to parents/guardians of children 6-23 months of age; 4) a process evaluation of the intervention implementation with the view to identify what worked (or did not work) and why; and 5) a description of the food environments in our study settings.

A. Research Procedures

Identification of role models: Positive deviance is a behavior change approach based on the observation that even in low-resource communities there are people who deviate towards preferred practices (“positive deviants”).²³ These individuals have uncommon, but successful, strategies that enable them to find better solutions than their peer.²³ Including role models in IYCF interventions can increase their effectiveness.²⁴⁻²⁶ With the assistance of community health workers (CHWs), we will identify “positive deviants” in the pilot villages from our formative work. These villages are culturally, linguistically, socially and economically similar to the villages included in our cRCT. In addition to the 8 scripted messages that we will use in this study (based on our pilot work), we will send an additional 8 unscripted role modeling messages, that describe strategies used by “positive deviants” to successfully adopt the key targeted behaviors. We will identify role models and record their messages in their villages between November 2021-May 2022.

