cRCT sample. The villages in which we are conducting this study are subsistence farming communities with high levels of poverty and malnutrition in three regions of Senegal: Thies, Diourbel and Fatick. Each of the 104 villages that will be included in the study have been purposively selected to ensure that they have an established farming group, and that they are sufficiently geographically dispersed in order to minimize risk of contamination. We will use the list of the household members of the farming groups of each of the 104 villages included in the cRCT as our sampling frame. Based on [name] previous experience, we will identify all households within the farming group that have a child 6-19 months of age at baseline (to ensure that the child is not >23 months at endline), and we will subsequently randomly select five mother, father and child triads to be included in our study sample. In some cases, the primary caregiver of the child may be a close relative rather than the birth mother. In these instances, the primary caregiver will receive the voice and text messages along with her husband or primary male caregiver. In total, we will sample 510 triads in 104 villages (~5 households/triads per village). Thus, our sample will include 510 mother, father and child triads. Baseline data collection will take place in May/Jun 2022, the intervention will be delivered between Jun-Sep 2022 and the endline data collection will take place in October 2022.

Process Evaluation sample: A smaller purposive sample of approximately 45 mothers and fathers, implementation project staff and CHWs will be included in Aim 2 of the project as part of the in-depth semi-structured interviews and focus groups conducted in the process evaluation. We will purposively select three villages from each region (n total = 9 villages) in order to maximize variation in village characteristics such as size, distance to urban settings, distance to markets, etc. Interviewees and focus group participants will be purposively selected from the list of all mothers and fathers receiving the voice messages in each of these villages to ensure variation in participant socio-demographics (e.g., household size, parity, age, etc.) as well as key people involved in the intervention's implementation. The process evaluation data collection will take place in between October and December 2022.

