Process questions captured by messaging platform & endline survey: At the end of each voice message, participants will be asked a series of yes/no questions related to the content of the message. More specifically, they will be asked: if they understood the message, if they found the message helpful and whether they intend to adopt the behavior. The response to the message will be keyed into the phone (1= yes; 2=no). In the event that a participant states that they did not understand the message, we will make note of it and then follow-up with them after the endline survey. There will also be an option to call a local number, for a member of the study team, to gain additional information. The OuA platform (<https://ouacompany.com>) being used in this study will track whether the call was answered, how long it was listened to and the answers to the questions relating to message understanding, helpfulness and intent to change behavior. These questions will help inform the process evaluation component of the study and will be used to inform the semi-structured interview/focus group questions. As part of the endline survey, we will include an unprompted open recall of the messages by mothers and fathers, in order to assess exposure to the intervention. We will also include questions related to program satisfaction. These questions have already been field tested as part of the piloting of this intervention.

Semi-structured interviews/focus groups: A sub-sample of mothers and fathers, as well project implementation staff and CHWs will participate in semi-structured interviews and focus group discussions to better understand the implementation process, including its strengths and weaknesses. The interviews will also be used to identify ways to integrate the messaging intervention into the existing activities of CHWs. The interview/focus group guides will be developed to gain insight into the fidelity, dose, reach, recruitment and context of the intervention. This will enable us to ascertain which aspects of the intervention worked and which aspects did not and why.

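### Parent interviewees for the process evaluation are not chosen by message exposure, so interviews with parents who seldom or never answered are not assured

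*Protocol*

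**What the plan says.** Protocol 1.3 A (Process Evaluation sample) and 4.1 A (Process evaluation) plan about 45 participants, made up of mothers and fathers, implementation staff and community health workers. Nine villages, three per region, are chosen to differ in size and in distance to towns and markets. On the parents, 1.3 A says: "Interviewees and focus group participants will be purposively selected from the list of all mothers and fathers receiving the voice messages". Section 4.1 A repeats this frame, with interviewees "purposively selected from the list of all mothers and fathers receiving the voice messages in each of these villages to ensure variation in participant socio-demographics", and names household size, parity and age as examples of the variation sought.

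Section 4.1 C places a further step after the endline survey: "Of those that indicate their willingness to participate, we will purposively select participants in order to ensure that we include variation", again in socio-demographic terms. Section 4.1 B shows that this is the second request: "We will obtain consent for participation in the process evaluation at the time of cRCT consent".

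The stated purpose in 1.3 is "a process evaluation of the intervention implementation with the view to identify what worked (or did not work) and why". The interview guides are to cover fidelity, dose, reach, recruitment and context, and 1.3 A says of the interviews: "This will enable us to ascertain which aspects of the intervention worked and which aspects did not and why".

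The messaging platform "will track whether the call was answered, how long it was listened to", and the endline survey includes unprompted recall of the messages by both parents as an exposure measure. Section 1.3 A says that the platform items will inform the process evaluation and the interview questions. It does not mention using them to choose interviewees. The SAP does not cover the process evaluation.

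**The concern.** Parents with little or no exposure are the first-hand informants on failed reach and low dose. The plan foresees how this might arise: 1.3 A (Intervention description) mentions areas of poor mobile coverage and parents who depend on another phone in the household. In a purposive sample, a characteristic that is not a selection criterion is left to chance. Here the individual-level criteria are socio-demographic and exposure is not among them.

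What is at stake is the qualitative part of Aim 2. If most interviewed parents were well reached, the account of barriers to delivery would be thin, and those barriers bear directly on the scale-up question that Aim 2 poses.

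**Working it through.** The plan states no figure on this point, so the check compares the relevant sections and sizes the pool.

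**1. Who is on the list.** The frame is parents *receiving* the messages, and the term is not defined. Elsewhere the Protocol uses *receive* for assignment: villages are randomised to receive the intervention or usual care (1.3 A, Randomization), the primary caregiver is to receive the messages (1.3 A, cRCT sample), and trial participants receive messages for 16 weeks (1.3 C). Nothing says that the list is filtered by answered calls. The likeliest meaning is the intervention-arm or send list, as opposed to control parents, who get the messages only after data collection. On that reading a parent who never answered is eligible. On a literal reading of confirmed receipt, that parent is excluded.

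**2. Who on the list can be picked.** Those who complete the endline survey and then agree. Parents lost before endline drop out of the pool.

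**3. What variation is sought.** Geographic variation at village level and socio-demographic variation at parent level. No section names answered calls, listening time or recall as a criterion.

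**4. What the other sources provide.** Call tracking and unprompted recall can show that a parent was not reached. They do not give the reason. The questions on understanding, helpfulness and intention come at the end of each voice message, so only someone who stays on the call gets to them. Parents who report not understanding are to be followed up around the endline survey; no equivalent follow-up is stated for parents who did not answer. Where a phone is shared, an answered call may not show which parent listened.

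**5. Timing.** Messages run from June to September 2022, endline is in October, and process interviews fall between October and December (1.3 A). The platform record therefore exists before interviewees are chosen.

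**6. Size of the pool.**
- Inputs: 9 villages (4.1 A), about 5 triads per village (1.5), 2 parents per triad.
- 9 x 5 x 2 = 90 parents, if all nine are intervention villages. The frame implies this, but the documents do not state it.
- Non-reach rate: not given. Assumed range 5% to 30%: 0.05 x 90 = 4.5 (about 5) and 0.30 x 90 = 27.
- Assume further that 30 of the 45 interviewees are parents, chosen without relation to exposure. The sampled fraction is 30/90 = 1/3, giving 4.5/3 = 1.5 to 27/3 = 9 unreached parents by chance, across three regions.

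The last line is illustrative only, because purposive selection among willing endline completers need not be unrelated to exposure. It shows that chance may supply some such interviews, or very few.

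**The case against.** The strongest reply is that the plan already handles non-reach. The platform and recall data are collected from participants generally, not only from interviewees, and 6.1 commits to a mixed-methods analysis of quantitative and qualitative process data. Staff and community health workers are interviewed too and can speak about delivery failures. Voice and text are combined expressly to cope with poor coverage, and phone ownership is said to be very high. The willingness step is unavoidable in any voluntary interview and renews consent already sought at enrolment. No outcome, estimand or power figure is touched.

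Most of this stands, and it rules out two stronger readings that a reader might infer:

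- *That unreached parents are ineligible.* This needs *receiving* to mean confirmed receipt, and the Protocol's own usage points to assignment.
- *That, after a null result, the evaluation could not tell ineffective messages from undelivered ones.* Call tracking and recall address that directly, and the platform data serve the process evaluation as well as the interview questions.

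Nor do the documents show that poorly reached parents would be less willing to be interviewed; that is conjecture.

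The reply does not supply the reason for non-reach from the parents concerned. Counts do not give it, and staff and health workers cannot report a parent's non-receipt first-hand.

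**Conclusion.** The point holds as a low-severity improvement to Aim 2. The list of eligible parents is undefined, though it probably means the intervention arm. Selection among them ignores exposure, so interviews with parents who seldom or never answered are possible but not assured. Non-reach will be measured; its explanation from the parents affected is what the plan leaves unsecured.

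The size cannot be fixed from the documents. The figure of about 5 to 27 unreached parents in a pool of about 90 rests on an assumed 5% to 30% non-reach rate and on all nine villages being intervention villages. The primary analysis and power are unaffected.

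**What to change.** In Protocol 1.3 A and 4.1 A and C:

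- Define the list as all intervention-arm mothers and fathers in the nine villages, as randomised, whether or not they answered calls.
- Add the platform's call-answer and listening record as a purposive selection variable beside the socio-demographic criteria, for example a set number of low- or non-answering parents per region. The tracking described covers calls, so the endline recall can serve as a second indicator for parents who may have had the text messages only.
- Keep the total at about 45.

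The SAP is dated May 2024 and the interviews were scheduled for late 2022. If they are complete, report the interviewees' platform exposure against that of the whole intervention arm and state the limitation.

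Cost: a wording change. The data are already collected and no interviews are added. The downside is that parents with low engagement may take more contact attempts.
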